6.3 Sample Size Justification

Approximately 50 subjects at up to 15 active sites will be enrolled in the CVT-ISR Trial. All subjects will be scheduled for clinical examination at six (6) months. The objective of the study is to assess the initial feasibility and performance of the CVT Everolimus-Coated PTCA Catheter in the treatment of subjects presenting in-stent restenosis in coronary arteries. The study is powered (per PASS13) based on the primary safety and effectiveness endpoints.

The primary safety endpoint for this analysis is freedom from target lesion failure (TLF) rate at 6 months post-index procedure, defined as a composite rate of all cardiac death, target vessel myocardial infarction and clinically-driven target lesion revascularization (TLR). The null (H0) and alternative (HA) hypotheses are:

H₀: ffTLF historical control \leq ffTLF _{CVT} treatment

H_A: ffTLF_{historical control} > ffTLF_{CVT treatment}

The proposed sample size of N=50 is based on the primary safety endpoint of freedom from TLF rate at 6 months post-index procedure. The sample size calculation is based on the following assumptions:

- A single comparison of CVT Treatment group to a safety OPC of 65%.
 - $\circ~$ A positive safety endpoint result would be where the lower limit of the 90% CI exceeded the OPC=65%
 - One-tailed α =0.05

The safety focus will be to estimate the frequency of TLF at six (6) months postprocedure and the associated 90% confidence interval.

If 8 of 50 (16%) subjects experience TLF, the point estimate for ffTLF is 84% and corresponding the 90% CI is [73%, 92%], well above the OPC of 65%.

By enrolling 50 subjects there is 95% power to detect a 19%-point margin over the Safety OPC, with a one-tailed α =0.05.

The primary effectiveness endpoint is late lumen loss at six (6) months. The null (H_0) and alternative (H_A) hypotheses are:

H₀: Late Loss historical control ≤ Mean Late Loss CVT treatment

HA: Late Loss historical control > Mean Late Loss CVT treatment
The power calculation is based on the following assumptions:

- A single comparison of CVT Treatment group to an historical control group.
- A true mean difference between the historical control group and the treatment group of 0.50 mm. This assumption is made based on the results of historical studies. Assuming the true mean late loss for the CVT treatment group is 0.30 mm, the difference between the control group and treatment group is calculated as: 0.80 mm 0.30 mm = 0.50 mm.
 - \circ Standard deviation is assumed to be 0.5 mm in the treatment group.
- Two-tailed α =0.10

Given the above assumptions, enrolling 25 subjects (analysis of 25 evaluable subjects) will provide 87% power for demonstrating CVT treatment's superiority over historical controls in LLL.

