6.4 Statistical Analyses

Detailed analyses of the primary endpoints will be performed when all of the subjects complete their primary follow-up visit at 180 days. No effort will be made to impute or extrapolate data to replace missing values. All calculations will be based on available data with missing data excluded.

Analysis of Primary Endpoints

The primary safety endpoint of freedom from target lesion failure (TLF) rate at 6 months post-index procedure will be analyzed using the safety population.

The analysis of the primary effectiveness endpoint of LLL at 6 months will utilize the evaluable populations.

Analysis of Secondary Endpoints

All secondary endpoints will be analyzed using descriptive statistics.

For binary variables, such as technical success counts, percentages and exact 95% confidence intervals using Clopper-Pearson's method will be calculated. For continuous variables, means, standard deviations, and 95% confidence intervals for the mean using the Gaussian approximation will be calculated. If the assumption of normality seems untenable, nonparametric methods will be employed instead.

For time-to-event variables, such as time to target lesion revascularization, survival curves will be constructed using Kaplan-Meier estimates.

Analysis of Other Data

The clinical laboratory values collected will be analyzed by tabulating the number and percentage of subjects with clinically significant changes from baseline for each parameter at each time point.

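### The stated 95% power for the primary safety endpoint does not match the plan's own decision rule: exact power is about 91% with 50 subjects analysed

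*Combined protocol and SAP*

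**What the plan says.** Section 6.3 ties the sample size to the safety endpoint: "The proposed sample size of N=50 is based on the primary safety endpoint of freedom from TLF rate at 6 months post-index procedure". The stated assumptions are:

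- The benchmark: "A single comparison of CVT Treatment group to a safety OPC of 65" per cent.
- The decision rule: "A positive safety endpoint result would be where the lower limit of the 90% CI exceeded the OPC=65" per cent.
- The error rate: "One-tailed α =0.05".
- A worked example with 8 failures in 50, for which "the point estimate for ffTLF is 84% and corresponding the 90% CI is [73%, 92" per cent].
- The power claim: "By enrolling 50 subjects there is 95% power to detect a 19%-point margin over the Safety OPC".

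No interval method or test is named for the primary safety endpoint; only the software is cited. For the secondary binary endpoints, Section 6.4 says "exact 95% confidence intervals using Clopper-Pearson's method will be calculated". On missing data, the same section says "All calculations will be based on available data with missing data excluded". Section 6.3 makes no allowance for attrition.

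**The concern.** The decision rule, the worked interval and the power figure should all describe the same test, and they do not. The printed interval implies one success cut-off and the printed power implies another, one event-free subject lower.

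Two things are at stake. First, the sample size is said to rest on this calculation, and it overstates the chance that a device performing as assumed meets its primary safety criterion. Second, a result of 38 of 50 event-free (76%) would be open to dispute: it meets the cut-off behind the stated power and fails the one behind the stated interval. That ambiguity on a primary endpoint should be removed before any data are seen.

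**Working it through.** **Inputs (all from Section 6.3).** n = 50; benchmark p0 = 0.65; assumed true rate p1 = 0.65 + 0.19 = 0.84; one-sided alpha 0.05; success if the lower limit of the two-sided 90% interval exceeds 0.65. The null and alternative hypotheses are printed there in the opposite direction to this rule; the calculation follows the rule.

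**Step 1: which interval is it?** 90% intervals for 42/50:

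| Method | Interval | Rounded |
|---|---|---|
| Clopper-Pearson | 72.98% to 91.78% | 73% to 92% |
| Wilson | 73.77% to 90.74% | 74% to 91% |
| Jeffreys | 74.14% to 91.03% | 74% to 91% |
| Wald | 75.47% to 92.53% | 75% to 93% |

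Only Clopper-Pearson gives the printed interval.

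**Step 2: the cut-off.** The Clopper-Pearson lower limit for x event-free subjects is the 5% quantile of a Beta(x, n − x + 1) distribution. For x = 38 it is 64.0%, which fails. For x = 39 it is 66.2%, which passes. Success therefore needs at least 39 of 50.

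**Step 3: exact size and power.** Size = P(X ≥ r | n = 50, p = 0.65). Power = P(X ≥ r | n = 50, p = 0.84).

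| Cut-off r | Size | Power |
|---|---|---|
| 38 | 6.61% | 95.2% |
| 39 | 3.42% | 90.7% |
| 40 | 1.60% | 83.4% |

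The plan's 95% is reproduced by r = 38, which breaches the stated 0.05 and fails the interval in Step 2. Under r = 39, the risk of missing the criterion at a true 84% is 100 − 90.7 = 9.3%. Reaching 95% power with r = 39 would need a true rate of 85.5%.

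**Step 4: does another method rescue 95%?** Wilson, Agresti-Coull and mid-p rules also give r = 39. Wald and Jeffreys rules give r = 38, with the 6.6% size.

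The usual normal approximation is Φ[(0.19 − 1.645·se0)/se1], with se0 = √(0.65·0.35/50) = 0.0675 and se1 = √(0.84·0.16/50) = 0.0518. It gives 93.6%, or 90.9% with a continuity correction. The arcsine formula gives 93.2%. Using only the alternative variance gives 97.8%, or 96.6% with the correction; using only the null variance gives 87.9%. None gives 95%.

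The most powerful test of size exactly 5% succeeds always at 39 or more, and at 38 with probability (0.0500 − 0.0342)/(0.0661 − 0.0342) = 0.494. Its power is 0.9071 + 0.494 × (0.9525 − 0.9071) = 93.0%. So no test of size 5% or less reaches 95% at n = 50. The smallest n at which the exact rule does is 55 (r = 42, size 4.9%, power 95.2%).

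**Step 5: fewer than 50 analysed.** Same rule, exact:

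| Analysed | Cut-off | Size | Power at 84% |
|---|---|---|---|
| 50 | 39 | 3.4% | 90.7% |
| 49 | 38 | 4.2% | 91.8% |
| 48 | 38 | 2.5% | 86.5% |
| 47 | 37 | 3.1% | 88.0% |
| 46 | 36 | 3.8% | 89.3% |
| 45 | 35 | 4.7% | 90.6% |
| 44 | 35 | 2.7% | 84.5% |

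Power moves in a saw-tooth because the cut-off is a whole number. No row reaches 95%.

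**The case against.** **The interval method is inferred.** This is true: Clopper-Pearson is named only for secondary endpoints, and the software option behind the power figure is not given. The 95% could come from a large-sample formula. But the conclusion does not turn on the inference. Every rule tried either gives about 91% or breaches the stated alpha, and 93.0% is the ceiling for any valid 5% test. What stands is that the source of the 95% cannot be established.

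**The plan plays down formal testing.** Section 6.1 calls this a feasibility trial in which significance is neither required nor enough for further study, and it mentions a trend at p ≤ 0.10. Section 6.3 puts the safety emphasis on estimation. A missed criterion is therefore not a decision to abandon the device. This limits the consequence, but not the error: Section 6.3 still sets a success criterion, specifies one-tailed 0.05 and bases the sample size on it. A one-sided threshold of 0.10 would give the 38 of 50 rule and 95.2% power, but that is not what the power sentence states.

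**The gap is small.** Power of 91% is still high, and a true rate only 1.5 points above the assumed 84% restores 95%. This stands, and it is why no change in sample size is needed.

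**Attrition is not a steady loss.** Losing one subject or five costs essentially nothing; losing two or six costs about 4 to 6 points. Attrition can lower power to roughly 84% to 87%, but need not.

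**Conclusion.** The concern holds. With 50 analysed, a true rate of 84% and the exact 90% interval that Section 6.3 illustrates, power is 90.7% and true one-sided size is 3.4%. The stated 95% is overstated by about 4 points and matches a cut-off whose type I error is 6.6%. The chance of missing the criterion under the planned assumption is about 9%, nearly twice the implied 5%.

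The figures rest on independent binomial outcomes and the 84% rate implied by the 19-point margin; the 90.7% also requires all 50 to be analysed. The identification of Clopper-Pearson rests on the worked example. This is a correction to a stated figure and an unnamed method that should be made; it does not undermine the design.

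**What to change.** In Section 6.3:

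1. Name the two-sided 90% Clopper-Pearson interval as the method for the primary safety endpoint, with success when its lower limit exceeds 65%.
2. State that with 50 analysed this means at least 39 event-free, with exact one-sided size 3.4% and exact power 91% at a true rate of 84%.
3. Say that the interval rule governs if the number analysed is not 50 (for example 38 of 48, or 36 of 46), and give the power for 44 to 49 analysed from the table above.

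Keep the sample size at 50. The cost is a few lines of text and a slightly less favourable power figure; no patients or procedures are added.

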6. STATISTICAL DESIGN AND ANALYSIS

6.1 Statistical Overview of the Trial

The primary sample size calculation is based on the hypotheses that the primary safety and effectiveness endpoints meet *a priori* specified Objective Performance Criteria (OPC).

The OPCs for the primary safety endpoint and effectiveness endpoints have been set using historical control data from thirty-two (32) published studies that evaluate treatments for ISR, analyzed in meta-analysis and also reviewed in a consensus document⁶. Since this is a feasibility trial, the attainment of statistical significance is neither a necessary nor a sufficient condition for determine whether the device merits further study. If the data exhibit a trend ($p \le 0.10$) toward statistical significance when compared to historical control and raise no safety concerns, it may be deemed worthy of further investigation. In addition, there will be a focus on estimating the magnitude of observed values at 180 days post-procedure and their associated 90% confidence

⁶ Jeger et al. Third International DCB Consensus Group Report JACC: Cardiovascular Interventions, 2020June;1 3(12):1391-402 Ae-Young Her et al. Current Management of In-Stent Restenosis, Korean Circ J. 2018 May;48(5):337-349 Leos Pleva et al. Treatment of coronary in-stent restenosis: a systematic review *J Geriatr Cardiol* 2018; 15: 173-184

intervals.

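### The 87% power stated for late lumen loss does not follow from the printed inputs: a one-sample test gives 99.9%, and no test, control SD or control sample size is given

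*Combined protocol and SAP*

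**What the plan says.** Section 6.3 frames the effectiveness hypothesis as superiority: historical late loss is greater than mean CVT late loss. It then lists what the calculation rests on:

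- The comparison: "A single comparison of CVT Treatment group to an historical control group".
- The effect: "A true mean difference between the historical control group and the treatment group of 0.50 mm", obtained as 0.80 mm minus 0.30 mm.
- The spread: "Standard deviation is assumed to be 0.5 mm in the treatment group". No SD is given for the controls.
- Alpha 0.10, two-tailed.

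The paragraph presents the power as the result of these inputs: "enrolling 25 subjects (analysis of 25 evaluable subjects) will provide 87% power for demonstrating CVT treatment's superiority over historical controls in LLL". The section cites PASS13 as the software but names no test or procedure.

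Section 6.1 bears on which test was meant: "The OPCs for the primary safety endpoint and effectiveness endpoints have been set using historical control data from thirty-two (32) published studies". It gives no patient count and no SD for those studies. Section 6.4 adds only the population: "The analysis of the primary effectiveness endpoint of LLL at 6 months will utilize the evaluable populations". Its remarks on Gaussian intervals and nonparametric methods come under secondary endpoints.

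**The concern.** With a difference equal to one SD and 25 subjects, a test against a fixed value should have power close to 100%, so 87% looks wrong at once. There are three possible explanations: the power figure is wrong, the difference or SD is misprinted, or the calculation used an input that was not printed.

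These have different consequences. If the SD is the misprint, late loss will be estimated less precisely than the text implies. If a control sample with its own variability was intended, the standard error and p-value at analysis differ from those of a comparison with a fixed criterion. Section 6.1 ties the judgement on further study partly to a p-value of 0.10 or less against historical control, so how that p-value is formed should be settled before the data are seen.

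**Working it through.** **Inputs (all from 6.3).** Difference d = 0.80 − 0.30 = 0.50 mm; SD s = 0.5 mm (treatment group); two-sided alpha 0.10; n = 25 evaluable. Stated power: 87%. A power within 2 percentage points of that counts as reproduced.

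**Step 1. One-sample t-test against a fixed 0.80 mm.**

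- Degrees of freedom: 25 − 1 = 24; critical t = 1.711.
- Noncentrality: (d/s) × √n = (0.50/0.5) × √25 = 5.
- Power from the noncentral t: 0.9993, or 99.93%. The normal approximation gives 99.96% and a 200,000-run simulation 99.93%.

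The stated 87% is not reproduced.

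**Step 2. Nearby one-sample readings.** The changed values here are assumptions.

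| Change to step 1 | Power |
|---|---|
| Two-sided alpha 0.05 | 99.8% |
| Two-sided alpha 0.01 | 98.1% |
| 20 evaluable | 99.6% |
| Signed-rank test at worst-case efficiency 0.864 (effective n = 0.864 × 25 = 21.6) | about 99.8% |

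At two-sided alpha 0.10, a one-sample test reaches 87% only with an SD of about 0.88 mm, a difference of about 0.285 mm, or about 9 subjects (86.2%). Each contradicts a printed input.

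**Step 3. Two-sample readings.** With m controls and a common SD, the noncentrality is d / (s × √(1/25 + 1/m)). Neither m nor a control SD is printed, so every control value below is an assumption.

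| Controls | Control SD (mm) | Test | Power |
|---|---|---|---|
| 12 | 0.5 | pooled t | 87.4% |
| 25 | 0.5 | pooled t | 96.7% |
| 50 | 0.5 | pooled t | 99.2% |
| 100 | 0.5 | pooled t | 99.8% |
| 25 | 0.70 | Welch t | 88.8% |
| 25 | 0.75 | Welch t | 86.1% |

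The first row, for example: 0.50 / (0.5 × √(1/25 + 1/12)) = 2.847 on 35 degrees of freedom, critical t 1.690, power 0.874.

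So 87% can be reached, but only with particular control values. The most obvious two-sample choice, 25 controls at the printed SD, gives 96.7%. A large control sample gives nearly the one-sample result.

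**Step 4. Precision on the printed inputs.** The expected half-width of the 90% confidence interval is t × s/√n: 1.711 × 0.5/5 = 0.171 mm with 25 evaluable, and 1.729 × 0.5/√20 = 0.193 mm if only 20 are evaluable.

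**The case against.** The best defence is that 6.3 never says one-sample. It compares safety with a stated criterion of 65%, but compares late loss with a historical control group, and it confines its SD to the treatment group. Both fit a control sample with its own variability, in which case 87% may be correct and the fault is incomplete reporting. That possibility stands. It does not rescue the paragraph, which offers 87% as the consequence of the listed inputs when the control SD and sample size it would need are not among them. Section 6.1 also says that the effectiveness criterion was preset, which makes the one-sample reading the more natural one.

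It is also fair that the test is only partly undefined. The hypotheses, direction, alpha, sample size and population are given; what is missing is the name of the test and whether the comparator is fixed or sampled. Nor is 0.80 mm labelled as the performance criterion anywhere. It appears only as the control term of the difference, so the sponsor should confirm it.

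Finally, Section 6.1 calls this a feasibility trial in which statistical significance neither decides nor is required for further study. That limits the consequence. It does not remove the need for a reproducible figure, because 6.3 says that the study is powered on both primary endpoints.

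**Conclusion.** The concern holds. On the printed inputs the power is 99.93% for a one-sample t-test against 0.80 mm, about 13 percentage points above the stated 87% (99.9 − 87 = 12.9). No nearby one-sample reading closes the gap, and two-sample readings that do so need control values absent from the documents. The one-sample conclusion assumes that the comparator is fixed at 0.80 mm, as Section 6.1 implies.

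The documents do not show which of the three explanations is right. On the printed inputs the discrepancy is conservative: the imaging subset is not underpowered, and the total of 50 rests on the safety endpoint. This should be fixed as a matter of reproducibility and of specifying the primary effectiveness test; it does not threaten the sample size.

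**What to change.** Recover the PASS output and reconcile the effectiveness paragraph of 6.3 with it. Name the test in both 6.3 and 6.4, say whether the comparator is a fixed criterion or a control sample, and list every input, including any control SD and sample size.

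If the printed inputs stand and the sponsor confirms a fixed 0.80 mm criterion, the text could read: one-sample t-test against 0.80 mm, true mean 0.30 mm, SD 0.5 mm, two-sided alpha 0.10, 25 evaluable subjects, power above 99%; expected 90% confidence interval half-width about 0.17 mm (about 0.19 mm with 20 evaluable).

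Otherwise, state the test and inputs that actually produced 87%. Values solved backwards from 87%, including the illustrative control values above, should not be inserted.

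The cost is one corrected paragraph in 6.3 and one sentence in 6.4. Enrolment and study procedures are unaffected.

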Record an image of the target lesion after pre-dilatation is completed. Ensure to perform an angiography distal to the target lesion. Assess the subject for any angiographic complications after pre-dilatation and confirm the lesion to be treated meets the study angiographic inclusion and exclusion criteria.

Successful pre-dilatation of the target lesion is defined as:

- Residual stenosis of <30% after pre-dilatation (per visual estimate) AND
- No major (>Grade B) flow-limiting dissection.

In case of unsuccessful pre-dilatation of the target lesion planned to be treated with the investigational device, the subject should be considered a screen failure and all lesions should be treated as per standard of care.

Treatment with CVT Everolimus-coated Catheter

It is recommended to select a CVT EVE-PTCA Catheter with a balloon length that allows for coverage of the targeted lesion plus approximately 2 mm additional coverage, by visual estimate, on each side of the lesion while not allowing the balloon length extend beyond the edges of the stent.

The balloon should be inflated for 60 seconds in order to allow for an optimal drug delivery to the surrounding tissue.

Post-Procedure Angiography Subset

A subset of twenty-five (25) subjects will complete post-procedure angiography assessment of the target vessel, as per the angiographic core laboratory guidelines, at 6 months post-procedure.

The 25 subjects undergoing angiographic follow up will represent the first subjects enrolled into the study, with no more than 15 patients undergoing angiographic follow up from a single site.

Note: The end of the procedure is defined as the time after a complete final angiogram has been performed and the last guidewire and catheter have been removed. In case the subject needs to return to the procedure room and a guiding catheter is reinserted for dilatation, this is considered a reintervention. Removal of the sheath(s) may be done at the Investigators discretion.

All catheters, including the CVT Everolimus-coated PTCA Catheter, should be delivered and deployed per their respective Instructions for Use (reference Appendix E for CVT Everolimus-coated PTCA Catheter IFU). All balloon inflations should be captured per the angiographic core laboratory guidelines.

Intravascular Ultrasound Examination (IVUS)

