6.2 Analysis Populations

The primary endpoints will be analyzed on the entire safety population and on the evaluable subject population, as appropriate.

The safety population will consist of all subjects who enrolled into the trial and for whom the procedure had been initiated.

All effectiveness endpoints will be analyzed using the evaluable population, which consists of subjects who had no bailout and at least one valid follow-up visit.

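### The late-loss sample size treats 25 assigned subjects as 25 evaluable, with no allowance for loss; this costs precision rather than power, and the stated 87% power does not follow from its inputs

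*Combined protocol and SAP*

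**What the plan says.** Section 6.3 states that "enrolling 25 subjects (analysis of 25 evaluable subjects) will provide 87% power" to show superiority over historical controls. Its inputs are:

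- comparator: the one treated arm is set against historical data, with no concurrent control
- effect: "A true mean difference between the historical control group and the treatment group of 0.50 mm", which is 0.80 mm minus 0.30 mm
- spread: "Standard deviation is assumed to be 0.5 mm in the treatment group"
- error rate: "Two-tailed α =0.10"

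Section 4.3 sets the number of films: "The 25 subjects undergoing angiographic follow up will represent the first subjects enrolled into the study", with a cap of 15 from any one site. Section 4.6 ties the 180-day imaging to the 25 subjects imaged at the index procedure. The IVUS group (15) and the OCT group (10) together make up those 25.

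Two rules then reduce the number. Section 6.2 analyses effectiveness in the evaluable population, "which consists of subjects who had no bailout and at least one valid follow-up visit". Section 6.4 rules out imputation: "All calculations will be based on available data with missing data excluded". However, the bail-out paragraph of Section 4.3 says that subjects who need bailout continue in the study and that their data stay in the statistical analyses. No section gives an expected loss rate, an inflation of the 25, or a replacement rule.

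**The concern.** The plan uses one number for two quantities: subjects assigned to repeat angiography and subjects with a usable late-loss value. They are equal only if none of the 25 dies, withdraws, declines the repeat catheterisation, has an unreadable film or, under Section 6.2, needs bailout. The documents foresee such losses. Section 3.11 provides for withdrawal and loss to follow-up, and Section 4.3 provides for bailout stenting. Appendix J puts dissection leading to ischaemia or infarction between 1% and 10%; that is not a bailout rate, but it makes zero an odd planning value.

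At stake is the precision of the primary effectiveness estimate. Section 6.1 says that statistical significance is not decisive in this feasibility trial and puts weight on estimated magnitudes with 90% confidence intervals. A smaller evaluable number widens that interval. The IVUS and OCT subsets have no reserve either.

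**Working it through.** **1. The plan's own figure.** Inputs from Section 6.3: difference 0.50 mm, SD 0.5 mm, two-tailed alpha 0.10, n = 25. The trial has one arm and a historical comparator, so the natural test is a one-sample t-test with noncentrality (0.50/0.5) × √25 = 5 and critical value t(0.95, 24). Power is 99.9% (0.9993). The normal approximation gives Φ(5 − 1.645) = 0.9996.

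The stated 87% is not reproduced. Other readings on the same inputs do not give it either:

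| Reading | Power |
|---|---|
| One-sample t, n = 9 | 86.2% |
| One-sample t, n = 10 | 89.8% |
| Two-sample t, 25 against 25 | 96.7% |
| Two-sample t, 25 in total split 12/13 | 78.2% |

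Some variants come within about one point, but only with inputs the plan does not state: the 12/13 split at one-sided alpha 0.10 (87.9%), or a two-sample rank test of 25 against 25 with efficiency 2/3 (88.1%).

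**2. Chance that all 25 are evaluable.** The documents give no loss rate, so the total loss d (every cause combined) is an assumption. With independent losses, P(all 25) = (1 − d)^25 and the expected evaluable number is 25(1 − d).

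| Assumed total loss d | P(all 25) | Expected evaluable |
|---|---|---|
| 2% | 60% | 24.5 |
| 5% | 28% | 23.75 |
| 10% | 7% | 22.5 |
| 20% | 0.4% | 20 |

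The chance falls below one half once d exceeds 1 − 0.5^(1/25) = 2.7%.

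**3. Precision and power at smaller n.** Half-width of the 90% interval = t(0.95, n − 1) × 0.5/√n. Power is the one-sample t power on the Section 6.3 inputs.

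| n | Half-width (mm) | Relative to n = 25 | Power |
|---|---|---|---|
| 25 | 1.711 × 0.1000 = 0.171 | 1.00 | 99.9% |
| 22 | 1.721 × 0.1066 = 0.183 | 1.07 | 99.8% |
| 20 | 1.729 × 0.1118 = 0.193 | 1.13 | 99.6% |
| 10 | not needed here | – | 89.8% |

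**4. Subsets, shrinking in proportion.** At 22 of 25: IVUS 15 × 0.88 = 13.2 and OCT 10 × 0.88 = 8.8. At 20 of 25: IVUS 12 and OCT 8.

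**5. What evaluable means.** Section 6.2 asks for a valid follow-up visit, not a film. A subject can belong to the evaluable population and still have no late-loss value; that subject drops out only through the missing-data rule in Section 6.4. The 25 evaluable subjects in Section 6.3 are therefore not the population that Section 6.2 defines.

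**The case against.** The strongest reply is that the shortfall hardly matters. On the plan's inputs power exceeds 99% at 20 evaluable, the interval widens by 0.012 to 0.022 mm against an assumed difference of 0.50 mm, and Section 6.1 does not make significance decisive. This stands, and it is why the point concerns a misstated size and its precision. A reader might infer that the late-loss comparison is underpowered; the stated inputs do not support that. The qualification is that 87% might rest on inputs the plan does not disclose. If 87% were right at n = 25 (a detectable difference of about 0.285 mm at SD 0.5), power would be 82.7% at 22 and 79.2% at 20.

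A reader might also infer that 25 evaluable subjects cannot be reached. With no loss rate in the documents, that certainty is unsupported: at 2% total loss a full 25 is more likely than not.

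Nor do the documents establish that every bailout is lost, because Section 4.3 contradicts Section 6.2. If bailouts stay in, missing films alone still produce the table in step 2.

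Finally, a reader might take it that a vacated slot can never pass to another subject. The plan is silent rather than prohibitive: the 15-per-site cap already lets slots move to later enrollees, and Section 4.3 can be read as a target of 25 completed films. Against that, Section 4.6 ties follow-up imaging to those imaged at index. It is also not clear that subjects outside the subset have agreed to a repeat film, since inclusion criterion 3 covers only what the plan requires of them.

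**Conclusion.** The point holds in a limited form. Section 6.3 equates assigned with evaluable and allows for no loss, so its evaluable size is unlikely to be reached at any total loss above about 2.7%. That conclusion rests on assumed loss rates and on independence between subjects. The consequence is a 90% interval about 7% wider at 22 evaluable and 13% wider at 20, with SD 0.5 mm as the plan assumes, and proportionately smaller IVUS and OCT subsets. Power on the stated inputs stays above 99% across that range. The same calculation shows that 87% does not follow from the figures printed beside it, which is the larger error in the sentence. The correction is worth making because the size is a relied-on figure and the repair is wording.

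**What to change.** 1. Restate Section 6.3 as 25 subjects assigned to follow-up angiography, with an explicit assumed loss rate and the evaluable number that results (for example 20 to 23).
2. At that number, give the 90% confidence interval half-width and the recomputed power, and name the test. If 87% came from other inputs, state them.
3. Define evaluable for late loss as having paired, readable index and 180-day films.
4. Reconcile the bail-out paragraph of Section 4.3 with Section 6.2, so that it is clear whether bailout subjects enter the late-loss analysis.
5. Consider reallocating unused imaging slots only after step 4, and never on a follow-up outcome such as death or revascularisation. A rule triggered by an unreadable index film would need a same-day core-lab reading, which the plan does not describe.

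Steps 1 to 4 change wording only and need no additional enrolment or films. The cost is that the stated evaluable size becomes slightly smaller.
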